9 STUDY POPULATION

Prospective approval of deviations from the eligibility criteria, also known as protocol waivers or exemptions, is not permitted.

9.1 Recruitment

Subjects will be recruited from CTC's database of healthy volunteers, as well as from strategic marketing campaigns. Advertisements in social media and other media (newspapers, internet, radio, local distribution of flyers, *etc.*) will be used to reach the target audience. The advertisement texts approved by the Independent Ethics Committee (IEC) will be used to create all materials (digital, radio and/or print) for recruitment.

9.2 Screening and enrollment log

Investigators must keep a record of all screened subjects even if they were not subsequently included in the study. This information is necessary to verify that subjects were selected without bias. The reason for screening failure should be stated for all subjects screened but not included. The reason for withdrawal should be stated for all subjects who were included but did not complete the study.

A screening number generated automatically in the electronic case report form (eCRF) will be allocated to each subject in connection with the informed consent process at the screening visit (Visit 1). The screening number will allow the identification of subjects irrespective of their possible eligibility for the study.

Eligible subjects will be assigned a 3-digit randomization number prior to the first IP use. If a subject is unable to receive the planned initial IP use within 28 days after screening (*i.e.*, the time interval between signing informed consent and the first IP use) the subject should undergo re-screening before continuing in the study.

9.3 Number of subjects

Approximately 76 subjects are planned to be screened with the aim of randomizing at least 43 subjects and achieving 38 evaluable subjects.

Efforts will be made to include at least 17 female subjects (approximately 40%). However, a minimum of 9 female subjects (approximately 20%) will be considered acceptable.

For the replacement of subjects who discontinue the study, see Section 9.8.3.

9.4 Inclusion criteria

For inclusion in the study, the subjects must fulfill the following criteria:

- 1. Willing and able to give written informed consent for participation in the study.
- 2. Subjects who have used Swedish snus and/or NP products for ≥1 year, with a minimum daily consumption of five pouches, and who are willing and able to use both oral tobaccobased and NP products while abstaining from other tobacco/nicotine products during the study.
- 3. Healthy male or female subjects aged 21 to 60 years, inclusive.
- 4. Medically healthy subject without abnormal clinically significant medical history, physical findings, vital signs, ECG, and hepatitis B/C and human immunodeficiency virus (HIV) results at the time of the screening visit, as judged by the Investigator.

5. Female subjects of childbearing potential must either practice abstinence from heterosexual intercourse (if this is their consistent practice) or agree to use a highly effective method of contraception with a failure rate of <1% to prevent pregnancy for the duration of the study.

The following are considered highly effective methods of contraception:

- combined (estrogen and progestogen-containing) hormonal contraception associated with inhibition of ovulation (oral, intravaginal, transdermal),
- progestogen-only hormonal contraception associated with inhibition of ovulation (oral, injectable, implantable),
- intrauterine device or intrauterine hormone-releasing system.

9.5 Exclusion criteria

Subjects must not enter the study if any of the following exclusion criteria are fulfilled:

- 1. A history of diagnosed hypertension or any cardiovascular disease, or ongoing manifestations of hypertension or any cardiovascular disease as judged by the Investigator.
- 2. Any surgical or medical condition, including abnormal salivation (also pharmaceutically induced), or history thereof, which, in the judgment of the Investigator, might interfere with the absorption, distribution, metabolism, or excretion of the IP or may either put the subject at risk because of participation in the study, influence the results, or the subject's ability to participate in the study.
- 3. A history of diagnosed severe allergy/hypersensitivity or ongoing manifestations of severe allergy/hypersensitivity to aroma compounds (including fragrances and/or flavorings), as judged by the Investigator.
- 4. Subjects with poor venous access or being scared of needles.
- 5. Any planned major surgery within the duration of the study.
- 6. Subjects who are pregnant, currently breastfeeding, or intend to become pregnant during the course of the study.
- 7. Any positive result at the screening visit for serum hepatitis B surface antigen, hepatitis B and C antibodies, and/or HIV.
- 8. Positive result for drugs of abuse or alcohol at the screening visit or on admission to the study site prior to IP use. Positive results that are expected given the subject's medical history and prescribed medications can be disregarded as judged by the Investigator.
- 9. History of alcohol abuse or excessive intake of alcohol, as judged by the Investigator.
- 10. Presence or history of drug abuse, as judged by the Investigator.
- 11. History of, or current use of anabolic steroids, as judged by the Investigator.
- 12. Current, ongoing use of beta-adrenergic blocking agents (beta blockers) or attention deficit hyperactivity disorder (ADHD) medications, including *pro re nata* (as needed) use.
- 13. Plasma donation within 1 month of screening or blood donation (or corresponding blood loss) until 3 months after the last IP use visit.

- 14. Subjects who intend to change their nicotine consumption habit, including the intention to stop using nicotine products, within the next 3 months of the screening visit, as judged by the Investigator.
- 15. The Investigator considers the subject unlikely to comply with study procedures, restrictions, and requirements.

9.6 Restrictions during the study

Subjects must be willing to comply with the restrictions as outlined in Sections 9.6.1 and 9.6.2.

9.6.1 General restrictions

- 1. Contraception requirements: Subjects of childbearing potential are expected to use contraceptive methods in accordance with inclusion criterion #5 or practice abstinence from heterosexual intercourse (if this is their consistent practice) during the clinical study.
- 2. Tobacco/nicotine products:

Subjects shall abstain from any self-administered oral tobacco/nicotine products as well as smoking (cigarettes and e-cigarettes) for at least 12 hours prior to IP use visits and during each IP use visit (Visits 2-6).

- 3. Mouth-related procedures: Subjects shall abstain from eating, drinking, or conducting any other mouth-related procedure (*e.g.*, tooth brushing) for 30 min prior to IP use, during IP use, and for 30 min after IP removal (Visits 2-6).
- 4. Drugs of abuse: Subjects shall abstain from any drugs of abuse during the study.
- 5. Alcohol: Subjects shall abstain from alcohol for at least 12 h prior to each visit from Visit 2 to the last visit (Visits 6).
- 6. Blood donation: The subjects must not donate blood or plasma within 1 month of screening until 3 months after the last IP use visit (Visit 6).
- 7. Participation in other clinical studies: The subjects are not allowed to participate in any other clinical study from the screening visit (Visit 1) until the last visit (Visit 6).

9.6.2 Prior and concomitant therapy

Use of any prescribed medication that includes beta-adrenergic blocking agents (beta blockers) or ADHD medications, including *pro re nata* use, is not allowed from the screening visit (Visit 1) until the last visit (Visit 6). As outlined in exclusion criterion #12, subjects currently using beta-adrenergic blocking agents or ADHD medications will be excluded from participation in the study.

There will be no other restrictions concerning concomitant medications or therapies, as long as the subject is on a stable course of medication from the screening visit to the last IP use visit (Visit 6). Prescribed medications taken *pro re nata* may be a reason for exclusion as judged by the Investigator if they affect the subject's general condition and salivation.

As detailed in exclusion criterion # 8, a positive drug screen will exclude a subject from participation in the study. However, positive results that are expected given the subject's medical history and prescribed medications (e.g., opioid analgesics) can be disregarded as judged by the Investigator.

9.7 Screen failures

Screen failures are defined as subjects who consent to participate in the clinical study but do not fulfill all eligibility criteria and are not subsequently included in the study. A minimal set of screen failure information is required to ensure transparent reporting of screen failure subjects. Minimal information includes documentation of signed and dated informed consent form (ICF) and reason(s) for screening failure.

Re-screening can be performed if any of the following were reasons for screening failure or non-randomization, as judged by the Investigator:

- Practical reasons.
- Non-significant medical conditions (*e.g.*, influenza, nasopharyngitis).
- Plasma or blood donation outside of the allowed time windows.
- Reserve subjects.

For subjects who are re-screened, a new screening number will be assigned and new, signed ICF must be collected.

9.8 Subject withdrawal

9.8.1 General withdrawal criteria

Subjects are free to discontinue their participation in the study at any time and for whatever reason without affecting their right to an appropriate follow-up investigation or their future care. If possible, the reason for withdrawal of consent should be documented.

Subjects may be discontinued from the study at any time at the discretion of the Investigator.

[figure not shown]
Reasons for discontinuation can include:

- AE (as judged by the Investigator and/or Sponsor).
- Death.
- Logistical problem.
- Lost to follow-up.
- Non-compliance with study schedule and restrictions.
- Physician decision.
- Pregnancy.
- Protocol deviation.
- Technical problems.
- Withdrawal of consent.
- Other.

9.8.2 Procedures for discontinuation of a subject from the study

A subject who prematurely discontinues participation in the study will always be asked about the reason(s) for discontinuation and the presence of any AEs. Any ongoing AEs will be followed up as described in Section 11.4.4.12.

The primary reason for discontinuation/early withdrawal must be specified in the eCRF and final drug accountability must be performed. If the reason for discontinuation was an AE, the AE must be specified in the eCRF.

9.8.3 Subject replacement

Subjects who are prematurely withdrawn prior to the start of IP use may be replaced at the discretion of the Sponsor.

9.9 Randomization

At Visit 2, subjects will be randomized to one of 10 use sequences using a Latin squares William's design balancing for first-order carry-over effects. The following sequences will be randomized:

- Sequence 1: A B E C D
- Sequence 2: B C A D E
- Sequence 3: C D B E A
- Sequence 4: D E C A B
- Sequence 5: E A D B C
- Sequence 6: D C E B A
- Sequence 7: E D A C B
- Sequence 8: A E B D C
- Sequence 9: BACED
- Sequence 10: C B D A E

where

A = NP 1 - Dry, flavor A - 3 mg

- B = NP 2 Moist, flavor B 3 mg
- C = NP 3 Moist, unflavored 3 mg
- D = T1 Tobacco-based snus 1 4 mg
- E = T2 Tobacco-based snus 2 8 mg

As this is an open-label study, the IP use sequence to which each subject is allocated will be recorded in the eCRF. Computer-generated randomization lists for each site will be created using the statistical analysis software (SAS) Proc Plan, SAS Version 9.4. The randomization lists will contain the site, subject number, randomization sequence, visit, and product.

The randomization list will be generated by CTC. The original randomization list will be kept by the randomizer and copies of the randomization list will be provided to each site and to the IP packing company.

10 INVESTIGATIONAL PRODUCTS

The IPs are supplied by Swedish Match.

10.1 Identity of investigational products

The IPs that will be used in the study are detailed in Table 10.1-1.

 Table 10.1-1
 Identity of investigational products and nicotine contents

IP	Nicotine content per pouch
NP 1 – Dry, flavor A	3 mg
NP 2 – Moist, flavor B	3 mg
NP 3 – Moist, unflavored	3 mg
T1 – Tobacco-based snus 1	4 mg
T2 – Tobacco-based snus 2	8 mg

10.2 Manufacturing, packaging, and labeling

All IPs are manufactured and packaged by Swedish Match in compliance with the Swedish law on food production. Production sites and batch IDs for the IPs will be documented in the trial master file (TMF).

IPs will be transferred from the original container, weighed, and individually packaged in identical sealed food-approved test containers at the Swedish Match analytical laboratory. The containers will be labeled with unique identification numbers by Swedish Match in accordance with the randomization lists. IPs will be shipped by Swedish Match directly to CTC.

10.3 Conditions for storage

All moist IPs (the two NP moist 3 mg products and the two tobacco-based products) will be stored under refrigerator temperature (4-8°C), while the dry IP (NP dry 3 mg product) will be stored in room temperature, both in access-controlled storage areas.

10.4 Preparation and accountability

The IPs will be dispensed according to the randomization list by the site personnel. The Investigator will maintain a storage and accountability log as well as a dispensing log detailing the dates and quantities of study IPs received, and used by each subject, as well as any IPs destroyed at the end of the study. Products deliberately and/or accidentally destroyed by the site, or the subject must be accounted for.

10.5 Investigational product use instructions

A single pouch will be administered in the morning of each IP use visit (Visits 2-6). Subjects will keep the pouch between their upper lip and gum for 30 min and will be instructed not to manipulate the pouch with the tongue or lips. They will be instructed not to eat, drink, chew gum, or brush their teeth for 30 min before, during use, and 30 min after the use of IP.

Subjects shall abstain from oral tobacco/nicotine products as well as smoking (cigarettes or ecigarettes) for at least 12 h prior to each IP use visit. To this end, subjects will be instructed to abstain from such products from approximately 20:00 (8 pm) the day before IP use visits (Visits 2-6). All IP uses will be performed during the morning hours (08:00 to 12:00) to facilitate abstinence.

10.6 Investigational product final accountability

Any IP not used, as well as all empty containers will be destructed at the site upon confirmation from the Sponsor. The Monitor will perform a final IP accountability reconciliation at the end of the study to verify that all unused IP is adequately destroyed and documented.

11 STUDY ASSESSMENTS

The study assessments are described in the sections below and the timing of assessments are detailed in the schedule of events (Table 8.1-1 and Table 8.1-2).

11.1 Recording of data

The PIs will provide the Sponsor with all data produced during the study from the scheduled assessments. They will ensure the accuracy, completeness, legibility, and timeliness of the data reported to the Sponsor in the eCRF and all required reports.

It is important that IP application and collection of PK blood sampling occurs as close as possible to the scheduled time points in Table 8.1-2. In order to achieve this, the timing priority order at a particular time point is:

- 1. Blood samples for PK
- 2. Pulse rate assessment
- 3. Visual analog scale (VAS) questions
- 4. MCQ

Allowed deviations from actual time points are outlined in Table 11.1-1 below.

-	IP use and collection	PK blood sampling (plasma)	Pulse rate (pulse oximeter)	VAS questions "craving" and "satisfaction"	VAS questions "product- liking" and "intent to use again"	MCQ
-00:15			$\pm 5 \min$			
-00:10		Pre-use sample can be		$\pm 3 \text{ min}^2$		
-00:01		taken at any time within 10 min prior to IP use.				
00:00	$\pm 0 \min$ (IP admin.)					
00:05		$\pm 2 \min$	$\pm 2 \min^1$	$\pm 3 \min$		
00:10		$\pm 2 \min$	$\pm 2 \min^1$	$\pm 3 \min$		
00:15		$\pm 2 \min$	$\pm 2 \min^1$	$\pm 3 \min$		
00:20		$\pm 2 \min$	$\pm 2 \min^1$	$\pm 3 \min$		
00:30	±1 min (IP collection)	$\pm 5 \min$	$\pm 5 \text{ min}^1$	$\pm 5 \min$	± 10 min	$\pm 10 \text{ min}$
00:40		$\pm 5 \min$	$\pm 5 \text{ min}^1$	$\pm 5 \text{ min}$		
01:00		$\pm 10 \text{ min}$	$\pm 10 \ min^1$	$\pm 10 \text{ min}$		
01:30		$\pm 10 \text{ min}$	$\pm 10 \ min^1$	$\pm 10 \text{ min}$		
02:00		$\pm 10 \text{ min}$	$\pm 10 \text{ min}^1$	$\pm 10 \text{ min}$		
04:00		$\pm 10 \min$	$\pm 10 \text{ min}^1$	$\pm 10 \text{ min}$		
06:00		± 10 min	$\pm 10 \text{ min}^1$	± 10 min		

 Table 11.1-1
 Allowed deviations from actual time points

1. Pulse rate should be measured prior to PK blood sampling if possible.

2. Only "craving" at -10 min.

11.2 Demographics and other baseline characteristics

11.2.1 Informed consent

Signed informed consent must be obtained before any screening procedures are initiated. The informed consent procedure is further described in Section 14.3.

11.2.2 Demographic information

The following demographic data will be recorded: gender, age, ethnicity, and race.

11.2.3 Medical/surgical history

Medical/surgical history will be obtained by subject interview to verify that the eligibility criteria are met.

11.2.4 History of nicotine use

History of oral tobacco/nicotine products use in terms of brands, average consumption per day during the last 30 days, duration of use (years, months), history of smoking in terms of number of cigarettes per day during the last 30 days, as well as history of vaping in terms of number of days during last 30 days, will be obtained by subject interview.

11.2.5 Eligibility criteria

Eligibility criteria should be checked during screening and verified before randomization and use of the first IP on Visit 2. The criteria are specified in Sections 9.4 and 9.5.

11.2.6 Height, weight, and body mass index

Weight and height will be measured without shoes. BMI will be calculated, with one decimal, from the recorded height and weight.

11.2.7 Physical examination

A physical examination will include assessments of the head, eyes, ears, nose, throat, skin, thyroid, neurological, lungs, cardiovascular, abdomen (liver and spleen), lymph nodes, and extremities.

11.2.8 Vital signs

Systolic and diastolic blood pressure and pulse will be measured at screening in a supine position after 10 min of rest.

Pulse rate assessments will be considered "normal" if within the following ranges:

-At screening (Visit 1): 40 to 90 beats per minute (bpm)

-During IP use visits (Visits 2-6): 40 to 100 bpm. Refer to Section 11.4.3.1.

11.2.9 Electrocardiogram

Single 12-lead ECGs will be recorded at the screening in a supine position after 10 min of rest using an ECG machine. The resting HR and PQ/PR, QRS, QT, and QTcF intervals will be recorded.

ECGs will be reviewed and interpreted on-site by the Investigator.

CONFIDENTIAL

11.2.10 HIV and hepatitis B/C

Subjects will be tested for HIV-1 and HIV-2 antibodies, HIV-1 p24 antigen, hepatitis B virus surface antigen, and hepatitis B and C virus antibodies prior to inclusion into the study. Any positive result will exclude the subject from participating in the study.

11.2.11 Pregnancy test

All females of childbearing potential will undergo a urine dipstick pregnancy test at the screening visit and at visits specified in Table 8.1-1. At Visits 3 to 6, pregnancy tests will be conducted only at the discretion of the Investigator.

11.2.12 Drug screen

Urine will be screened for drugs of abuse at time points outlined in the schedule of events (Table 8.1-1) using the Drug Screen Multi-15 Dip Test. Additional random tests may be conducted during the study period at the discretion of the Investigator.

11.2.13 Alcohol test

Urine alcohol tests will be performed at the time points outlined in the schedule of events (Table 8.1-1 and Table 8.1-2). Additional random tests may be conducted during the study period at the discretion of the Investigator.

11.2.14 Baseline symptoms

A baseline symptom is defined as an event that occurs between the subject's signing of the ICF and the first use of IP (*i.e.*, an event that occurs during the screening period). Such events are not AEs but will be recorded as baseline symptoms in the AE Log in the eCRF.

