Aside from the risks related to the IPs, as detailed above, there may also be risks related to the medical devices used in the study (*e.g.*, indwelling venous catheters). However, these devices are used in routine medical care and the risk associated with their use is considered low and ethically justifiable. The repeated blood sampling for PK analysis will be conducted during a 3-week period to give sufficient time between each blood sample occasion. Study-specific evaluations and sampling procedures, such as blood pressure measurements using a blood pressure cuff (at screening) and frequent blood sampling (during Visits 2-6), may cause transient discomfort. However, the risk is deemed to be low and ethically justifiable. Overall, the combined safety data from previous pre-clinical and clinical studies have not revealed any safety issues that would outweigh the expected benefits of the study.

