11.4.4 Adverse events

The PIs are responsible for ensuring that all medical staff involved in the study are familiar with the content of this section and the content of the CTC standard operating procedures (SOPs) regarding emergencies.

AEs will be handled in accordance with applicable regulations and guidelines [10].

For the purpose of this study, AEs will be assessed in relation to the IPs starting from the first IP use.

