11.4.4.1 Definition of adverse event

An AE is defined as any untoward medical occurrence in a subject to whom a medicinal product is administered, and which does not necessarily have a causal relationship with this IP use.

An AE can be any unfavorable and unintended sign (including an abnormal laboratory finding), symptom, or disease temporally associated with the use of a medicinal product, whether or not considered related to the medicinal product.

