11.4.4.3 Time period and frequency for collecting adverse events

All AEs (including SAEs) will be collected from the start of first IP use until the last visit (Visits 2-6).

Any AE with a start date on the day of each IP use must be recorded with the start time.

On the last IP use visit (Visit 6), information on new AEs or SAEs, if any, and stop dates for ongoing events must be recorded as applicable.

Investigators will not be obliged to actively seek AEs or SAEs after conclusion of the study participation. However, if the Investigator learns of any SAE, including a death, at any time after a subject has been discharged from the study, and they consider the event to be reasonably related to the study intervention or study participation, the Investigator must promptly notify the Sponsor.

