11.4.4.8 Assessment of causal relationship

The Investigator must assess the causal relationship between an AE and the use of the IPs using the definitions below. Each assessment should be recorded in the AE Log of the eCRF.

Probable	The event has a strong temporal relationship to the IP or recurs on re- challenge and another etiology is unlikely or significantly less likely.		
Possible	The event has a suggestive temporal relationship to the IP, and an alternative etiology is equally or less likely.		
Unlikely	The event has no temporal relationship to the IP or is due to underlying or concurrent illness or effect of another drug (i.e. , there is no causal relationship between the IP and the event).		

An AE is considered causally related to the use of the IP when the causality assessment is probable or possible.

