11.4.4.11 Reporting of serious adverse events

The Investigator must report SAEs within **24 h** of awareness to the Sponsor or its designee, this includes both initial information and any subsequent relevant/significant follow-up information to a previously reported SAE. The primary mechanism for reporting an SAE will be via the eCRF. When the Investigator classifies the event as "serious" in the eCRF, and signs off the event, an automatic e-mail alert is sent to the Sponsor or its designee, and any other pre-defined recipients.

The backup procedure for reporting an SAE in case the eCRF is unavailable will be via the paper SAE form provided in the Investigator Site File (ISF). The Investigator must fill in the SAE form and send it Sponsor or its designee. The study site must notify the site Monitor via phone or e-mail about the submission of the SAE report. As soon as the site personnel have access to the eCRF, the SAE must be reported electronically as well. The completed, signed, and dated paper SAE form should, within 24 h, be scanned and delivered via encrypted e-mail or secure file transfer to:

A copy of the SAE paper form must also be delivered via encrypted e-mail or secure file transfer to CTC at:

All available information regarding the SAE must be entered in the AE Log for the specific subject, *i.e.*, AE term, intensity, causality, outcome, seriousness criteria, action taken with IP, and a narrative including the Investigator's rationale for the causality assessment.

The SAE report will be reviewed by the Sponsor or its designee to ensure that the report is valid. The Sponsor or its designee will acknowledge receipt of the SAE report to the reporting Investigator. For SAEs where important or relevant information is missing, follow-up queries to the site are raised promptly to keep the regulatory reporting timelines.

The Sponsor will perform an independent assessment of causality, including a rationale for the assessment. The causality assessment given by the Investigator should not be downgraded by the Sponsor. If the Sponsor disagrees with the Investigator's causality assessment, the opinion of both the Investigator and the Sponsor should be provided in the report.

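### Serious events between consent and the first pouch are classed as baseline symptoms, so the 24 h SAE report is not required even when a study procedure caused them

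*Protocol*

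**What the plan says.** Section 11.2.14 of the protocol defines a baseline symptom as "an event that occurs between the subject's signing of the ICF and the first use of IP" and then rules: "Such events are not AEs but will be recorded as baseline symptoms in the AE Log in the eCRF". Nothing in that section separates serious from non-serious events, or procedure-related events from others. A footnote to Table 8.1-2 places baseline symptoms at Visit 2 as well, up to the first use.

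The AE sections use the same boundary. Section 11.4.4 states that "AEs will be assessed in relation to the IPs starting from the first IP use". Section 11.4.4.3 states: "All AEs (including SAEs) will be collected from the start of first IP use until the last visit (Visits 2-6". Section 11.4.4.1 defines an AE as "any untoward medical occurrence in a subject to whom a medicinal product is administered". Section 11.4.4.6 requires a seriousness assessment for each AE. Section 11.4.4.11, which begins "The Investigator must report SAEs within", sets a 24 h limit for reporting to the sponsor.

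On procedure risk, section 6.3.1 says that "there may also be risks related to the medical devices used in the study", gives indwelling venous catheters as its example, and mentions frequent blood sampling. It rates these risks as low.

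**The concern.** Consent, not the first pouch, is the point from which the study exposes a subject to its procedures. If a serious event caused by one of those procedures is by definition not an AE, no later step of the safety process has to be applied to it. The sponsor would then depend on the site volunteering the information. What is at stake is subject protection in healthy volunteers who, by section 6.3.2, gain no direct benefit beyond a brief medical examination. The protocol would also treat one event in two ways, depending only on whether it came before or after the first pouch.

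**Working it through.** The plan states no figure to reproduce. The check is a cross-reading of the sections, followed by a count of exposures.

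**Which study procedures precede the first pouch?**

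- Screening serology is drawn before inclusion (11.2.10; one sample in Table 12.2-1).
- The Visit 2 pre-use PK sample is taken 10 to 1 minutes before use. PK samples are drawn through an indwelling catheter (11.3.1), so the catheter is taken to be in place by then.

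**Does a serious event in that window reach the sponsor by obligation?**

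1. By 11.2.14 it is a baseline symptom and not an AE.
2. By 11.4.4 and 11.4.4.3, AE and SAE collection has not started.
3. By 11.4.4.6, seriousness is assessed for AEs, so this event need not be assessed.
4. By 11.4.4.11, the 24 h duty attaches to SAEs, so it does not apply.

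No other section imposes an expedited report for this window.

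**How is the same event treated at other times?** Take a hospital admission after a faint at catheter placement.

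| Timing | Status under the protocol | 24 h report or prompt notification |
|---|---|---|
| Visit 2, before the pouch | Baseline symptom (11.2.14) | Not required |
| Visits 3 to 6 | SAE (11.4.4.2, 11.4.4.3) | Required within 24 h (11.4.4.11) |
| SAE learned of after discharge, judged reasonably related to taking part in the study | SAE (11.4.4.3) | Prompt notification required |

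The third row shows that the protocol accepts relation to participation, and not only to the product, as grounds for notification. Section 11.4.4.6 likewise uses consent as its boundary when it exempts planned admissions for conditions that existed before the form was signed.

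**Extent of the gap**

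- Screening draws: about 76 (planned number screened, 9.3).
- Catheter placements: 43 randomized × 5 visits = 215, assuming one per visit. Those before first use: 43 × 1 = 43, and 43 / 215 = 20%. The other 215 − 43 = 172 (80%) lie wholly inside the AE and SAE window.
- Duration: up to 28 days from consent to first use; beyond that, 9.2 calls for re-screening.

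For the 43 Visit 2 catheters, only the time before the pouch is outside the window. The protocol gives no event rate, so these counts cannot be turned into expected events.

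**The case against.** The strongest reply is that this is a coherent choice. Sections 11.2.14, 11.4.4, 11.4.4.1 and 11.4.4.3 agree that AEs belong to product use and start there. That is a legitimate way to collect product-related AEs, and it stands for non-serious events. It does not explain why a serious event caused by a study procedure should carry no duty to report.

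Second, section 11.4.4.11 refers to a safety management plan, which is not shown and might add a rule. That is possible. But it is described as detailing the handling of SAEs, and under the protocol these events are not SAEs.

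Three stronger readings are tempting, and the document does not support them.

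- A reader might infer that the trial cannot report on the catheter risk, or that neither sponsor nor ethics committee would learn of an event. In fact the events are entered in the AE Log of the eCRF, where seriousness can be marked and where classifying an event as serious triggers the alert to the sponsor. Reasons for screening failure or withdrawal are also recorded (9.2, 9.7, 9.8.2). The duty is missing, not all visibility.
- A reader might infer that procedure-related events after first use fit no causality category, because the Unlikely category in 11.4.4.8 reads "The event has no temporal relationship to the IP or is due to underlying or concurrent illness or effect of another drug". The definition continues with a gloss that there is no causal relationship between product and event. An investigator who attributes a faint to the catheter can therefore choose that category.
- A reader might add the 12 h abstinence as a source of serious events. Section 6.3.1 does not name it as a risk; it mentions abstinence only in explaining why nicotine exposure should be lower at the visits.

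**Conclusion.** The point holds as a gap in the reporting duty. As written, the protocol does not require a seriousness assessment or a 24 h report for a serious event caused by the screening draw or by the Visit 2 catheter and pre-use sample. This is an explicit exclusion, not detail left for another document.

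The gap covers about 76 draws and 43 of 215 catheter placements (20%), with serious events presumably rare. The conclusion assumes one catheter placement per visit, in place before the pre-use sample, and no overriding rule in the unseen safety management plan. It has no bearing on Cmax, the equivalence analysis or the sample size. It is worth correcting because it concerns subject protection and the correction is small.

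**What to change.** Amend sections 11.2.14, 11.4.4 and 11.4.4.3 together. From signature of the consent form, serious events, at minimum those judged related to a study procedure, should be assessed for seriousness and reported to the sponsor under the existing 24 h process. State that this applies even though no product has yet been used, so that the product-based definition in 11.4.4.1 does not cancel it. All other events before first use can remain baseline symptoms. Events reported under the new rule belong to no product, so list them separately from the by-product AE tables in 17.7.5.

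The cost is a few sentences and at most a few extra SAE reports. The AE Log and the alert already exist. The sponsor should confirm that the seriousness field can be completed for a baseline-symptom entry.
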